9. BIOMARKER

Serum and plasma will be collected according to the Study Schedule of Activities for biomarker analysis. More details of the biomarker analysis will be provided in a separate document.

10. INTERIM ANALYSIS

No interim analysis for claiming efficacy is planned. Interim safety review will be conducted by a Data Monitoring Committee (DMC). The analysis will be performed by a designated CRO. Details are in DMC charter and DMC SAP.

11. CHANGES FROM ANALYSES PLANNED IN THE PROTOCOL

11.1. Changes from Protocol

Analysis in the SAP	Analysis planed in the protocol	Reason
Section 5.2.2.3 Changes in SF-6D utility index score.	Section 7.2.2 Change in the SF-6D 6 domain scores and the utility index.	The 6 domains were not generated for analysis by the Optum software. They were used to calculate the utility index score only.
Section 5.2.3.1 Time to pain response, defined as number of days from fist dose to the first day a subject's daily pain NRS is ≤ 2 of the 3 days over which, the rolling average daily pain NRS is ≤ 2 .	Section 7.3.1 Time to pain response defined as a rolling average of NRS score of 2 or less on three consecutive days.	A score of 3 or higher on the first day of the rolling average should not qualify pain response.
Section 5.2.3.1 Time to treatment response defined as time from first dose to the first day of pain response, and CRP ≤ 0.5 within 7 days before or after pain response. Treatment response day will be the first day that the above criterion is met. If pain response occurs before CRP ≤ 0.5 , each 3-day rolling average of NRS should be ≤ 2.0 from the day of pain response to the day of CRP ≤ 0.5 . The response day will be the day of pain response. If CRP ≤ 0.5 occurs before pain response, the response day will also be the day of pain response.	Section 7.3.1 Time to clinical response (monotherapy + NRS ≤ 2 + CRP ≤ 0.5 mg/dL)	Subjects were enrolled with a qualifying episode and on background therapy. The endpoint of interest is to evaluate how soon subjects will reach response in both pain and CRP after initiating riloncept while on background therapy.

11.2. Impact of COVID-19 Pandemic

The KPL-914-C002 study was nearing the end of Randomized Withdrawal (RW) phase of the study when COVID-19 pandemic started. The impact of the pandemic to the study conduct is limited. A separate document will be prepared to summarize any protocol deviations which occurred as a result of the pandemic.

There are no special data handling rules and analyses implemented for COVID-19 related protocol deviations.

Pericarditis Concomitant medication tapering					X	X	X	X	X	
Full Physical Examination ^c	X									
Abbreviated Physical Examination ^d		X								X
Body weight and height		X								X
12-Lead ECG		X								X
Echo ^e		X ^e								X ^e
MRI (substudy only)		X								
Pericardial pain (11-point NRS)	X ^f									DAILY ^g

Statistical Analysis Plan

Kiniksa Pharmaceuticals, Ltd.
Study KPL-914-C002

Trial Period	SCREENING ^a	RUN-IN (12 weeks) ^m								
		ENROLLMENT			RANDOMIZATION ^{-q}					
Visit Name	Screening Visit	RI Baseline	RI Day 2	RI Day 4	RI Week 1	RI Week 2	RI Week 4	RI Week 6	RI Week 10	RI Week 12/ RW Baseline
Visit Window ^b (days)	(-28)	NA	NA	+/- 1	+/- 2	+/- 2	+/- 2	+/- 2	+/- 2	+/- 3
Visit Type	Clinic	Clinic	Clinic	TC/RN	TC/RN	TC/RN	TC/RN	Clinic	TC	Clinic
EQ-5D		X								X
SF-36		X								X
ISI		X								X
PGIPS		X						X		X
PGA-PA		X						X		X
Hematology, Chemistry Labs (Central)		X						X		X
Lipid Panel (Central) ^h		X								X
CRP (Local)	X ^f									X
CRP (Central)	(X)	X		X	X	X	X	X		X
Hematology, Chemistry, IGRA ^t , hepatitis serology, HIV (Local)	X									
Chest X-Ray	X									
Urine Pregnancy (Local or Central) ^j	X	X								
Urinalysis (Central)		X								
PK (Central) ^s			X ⁱ		X	X	X			
ADA (Central) ^s		X				X		X		
Biomarkers (Central)		X			X		X			
Pharmacogenomics Informed Consent ^k		X								
Pharmacogenomics Sampling (Central) ^k							X			
IWRS Subject Status Update	X	X								X
IWRS Weight Input (pediatric only)		X								X

Statistical Analysis Plan

Kiniksa Pharmaceuticals, Ltd.
Study KPL-914-C002

Trial Period	SCREENING ^a	RUN-IN (12 weeks) ^m								
		ENROLLMENT								RANDOMIZATION ^{-q}
Visit Name	Screening Visit	RI Baseline	RI Day 2	RI Day 4	RI Week 1	RI Week 2	RI Week 4	RI Week 6	RI Week 10	RI Week 12/ RW Baseline
Visit Window ^b (days)	(-28)	NA	NA	+/- 1	+/- 2	+/- 2	+/- 2	+/- 2	+/- 2	+/- 3
Visit Type	Clinic	Clinic	Clinic	TC/RN	TC/RN	TC/RN	TC/RN	Clinic	TC	Clinic
IWRS Drug Dispensing		X		X				X		X
In Clinic Study Drug Administration ^o		X ⁿ						X		X
Outpatient Study Drug Administration ^o					WEEKLY					
Study Drug Compliance Review		X			X	X	X	X	X	X
Clinical Response Evaluation										X ^p
Adverse Event Reporting ^l	X	X		X	X	X	X	X	X	X

a The screening and enrollment visit can be combined.

b Scheduling of visits within visit windows requires cautious planning to ensure there is no interruption to subject evaluation and study drug treatment.

c Full physical examination includes at minimum evaluation of vital signs, head, eye, ear, nose, and throat as well as cardiovascular, dermatological, musculoskeletal, respiratory, GI, genitourinary, and neurological systems. The decision to perform examination of genitourinary system should be guided by clinical judgement.

d Abbreviated physical examination includes at minimum evaluation of vital signs, lung and heart sounds, including evaluation for pericardial rub.

e ECHO is required to be obtained according to the central core lab parameters and then read locally and submitted to the central core lab for separate review and analysis.

f Both a documented CRP ≥ 1.0 mg/dL AND a pericarditis pain level of ≥ 4 is required 7 days prior to and including the Run-In Baseline visit. These are not required to occur on the same day.

g Subjects missing ≥ 4 daily pain measurements during the 7 days prior to and including the Randomization Withdrawal baseline visit will be unable to proceed to randomization due to lack of data required for treatment response evaluation.

h Lipid panels are non-fasting and are to be drawn at a minimum of every 6months during the randomization withdrawal and LTE periods, or more frequently as needed, with mandated evaluations as detailed in the schedule of events.

i Applicable to 24-hour post dose PK sub-study participants only.

j For women of child bearing potential - urine pregnancy testing can be repeated as needed throughout the course of the study and serum pregnancy can be drawn as needed; urine pregnancy is required to be performed at enrollment and 6 weeks after the last dose of study drug.

k Pharmacogenomics informed consent and subsequent sampling can be performed at any time in the study however, it is preferable to have this completed at the beginning of the study.

l Adverse event reporting begins following the subject providing informed consent.

m All procedures are to be completed prior to study drug administration.

Statistical Analysis Plan

Kiniksa Pharmaceuticals, Ltd.
Study KPL-914-C002

-
- n The first dose of study drug is a loading dose. Adult subjects receive 2 SC doses 160 mg (total 320 mg); pediatric subjects (subjects ≥ 12 and < 18 years of age) receive 2 SC doses of 2 x 2.2 mg/kg.
 - o Study drug administration is once weekly with a minimum of 5 days required between doses.
 - p Randomization and subsequent study drug dispensing to occur after confirmation of Clinical Response (see definition of Clinical Response in Section 6.2.2).
 - q The Randomization visit serves as both the RI Week 12 visit and the RW baseline visit.
 - s PK and ADA samples will be collected prior to study drug administration. PK at enrollment/baseline will be taken from ADA

Statistical Analysis Plan

Kiniksa Pharmaceuticals, Ltd.
Study KPL-914-C002**Table 5: Study Schedule of Activities – Randomized Withdrawal**

Trial Period	RANDOMIZED WITHDRAWAL (event-driven) ^m								END OF RANDOMIZED WITHDRAWAL (EORW) ^t
	RW Week 4	RW Week 8	RW Week 12	RW Week 16	RW Week 20	RW Week 24	RW Every 8 Weeks	RW Every 8 Weeks	
Visit Window ^b (days)	+/- 2	+/- 2	+/- 2	+/- 2	+/- 2	+/- 2	+/- 2	+/- 2	+/- 7
Visit Type	TC/RN	Clinic	TC/RN	Clinic	TC/RN	Clinic	TC/RN	Clinic	Clinic
Informed Consent Form									X
Concomitant medications	X	X	X	X	X	X	X	X	X
Pericarditis Concomitant medications	X	X	X	X	X	X	X	X	X
Full Physical Examination ^c						X			X
Abbreviated Physical Examination ^d									
Body weight and height		X		X		X		X	X
12-Lead ECG						X			X
Echo ^e						X ^e			X ^e
MRI (substudy only)						X			
Pericardial pain (11-point NRS)	DAILY								
EQ-5D						X			X
SF-36						X			X
ISI						X			X
PGIPS		X		X		X		X	X
PGA-PA		X		X		X		X	X
Hematology, Chemistry Labs (Central)		X				X		X	X
Lipid Panel (Central) ^h						X			X
CRP (Local)									

Statistical Analysis Plan

Kiniksa Pharmaceuticals, Ltd.
Study KPL-914-C002

Trial Period	RANDOMIZED WITHDRAWAL (event-driven) ^m								END OF RANDOMIZED WITHDRAWAL (EORW) ^t
Visit Name	RW Week 4	RW Week 8	RW Week 12	RW Week 16	RW Week 20	RW Week 24	RW Every 8 Weeks	RW Every 8 Weeks	Per Announced End Date ^u / LTE-Baseline
Visit Window ^b (days)	+/- 2	+/- 2	+/- 2	+/- 2	+/- 2	+/- 2	+/- 2	+/- 2	+/- 7
Visit Type	TC/RN	Clinic	TC/RN	Clinic	TC/RN	Clinic	TC/RN	Clinic	Clinic
CRP(Central)	X	X	X	X	X	X	X	X	X
PK (Central)		X				X			X
ADA (Central)						X			X
Biomarkers (Central)		X				X			
Urine Pregnancy ^j (Local or Central)									X
Urinalysis									X
IWRS Subject Status Update									X
IWRS Weight Input (pediatric only)		X		X		X		X	X
IWRS Drug Dispensing		X		X		X		X	X ^v
In Clinic Study Drug Administration ^o		X		X		X		X	X ^v
Outpatient Study Drug Administration ^o	X	WEEKLY							
Study Drug Compliance Review	X	X	X	X	X	X	X	X	X
Assessment of Pericarditis Recurrence	X	X	X	X	X	X	X	X	X
Adverse Event Reporting ^l	X	X	X	X	X	X	X	X	X

b Scheduling of visits within visit windows requires cautious planning to ensure there is no interruption to subject evaluation and study drug treatment.

c Full physical examination includes at minimum evaluation of vital signs, head, eye, ear, nose, and throat as well as cardiovascular, dermatological, musculoskeletal, respiratory, GI, genitourinary, and neurological systems. The decision to perform examination of genitourinary system should be guided by clinical judgement.

Statistical Analysis Plan

Kiniksa Pharmaceuticals, Ltd.
Study KPL-914-C002

-
- d Abbreviated physical examination includes at minimum evaluation of vital signs, lung and heart sounds, including evaluation for pericardial rub.
 - e ECHO is required to be obtained according to the central core lab parameters and then read locally and submitted to the central core lab for separate review and analysis.
 - h Lipid panels are non-fasting and are to be drawn at a minimum of every 6months during the randomization withdrawal and LTE periods, or more frequently as needed, with mandated evaluations as detailed in the schedule of events.
 - j For women of child bearing potential - urine pregnancy testing can be repeated as needed throughout the course of the study and serum pregnancy can be drawn as needed; urine pregnancy is required to be performed at enrollment and 6 weeks after the last dose of study drug.
 - l Adverse event reporting begins following the subject providing informed consent.
 - m All procedures are to be completed prior to study drug administration.
 - o Study drug administration is once weekly with a minimum of 5 days required between doses.
 - s PK and ADA samples will be collected prior to study drug administration. PK at enrollment/baseline will be taken from ADA. As required, ADA samples will be collected at EOS, ET, and Unscheduled visits.
 - t The EORW visit serves as both the last visit of the RW period and the baseline visit of the LTE period.
 - u For all subjects, the final clinic visit of the end of RW period is to be scheduled once the End of the Randomization Withdrawal end date is announced by Sponsor. This includes subjects that are taking blinded study drug, open-label rilonacept, or who have prematurely discontinued study drug.
 - v Study drug administration to occur only after subject provides informed consent for the open-label extension period.

Table 6: Study Schedule of Activities – Long Term Extension

Trial Period	LONG TERM EXTENSION (up to 24 months)			
	Long Term Extension Treatment (up to 24 Months)^m			
Visit Name	LTE Week 12	LTE Week 24	LTE Every 12 Weeks	LTE 18-month Assessment
Visit Window^b (days)	+/- 2	+/- 2	+/- 2	18 months from most recent recurrence
Visit Type	Clinic	Clinic	Clinic	Clinic
Concomitant medications	X	X	X	X
Pericarditis Concomitant medications	X	X	X	X
Full Physical Examination ^c		X		X
12-Lead ECG		X		X
Echo ^e		X		X
MRI		X ^z		X ^z
EQ-5D		X		
SF-36		X		
ISI		X		
PGIPS	X	X	X	
PGA-PA	X	X	X	
Hematology, Chemistry Labs (Central)	X	X	X	
Lipid Panel (Central) ^h		X		
CRP (Central)	X	X	X	X
PK (Central)		X		X
ADA (Central)		X		
Biomarkers (Central)		X		
Urine Pregnancy ^j (Local or Central)		X		X
Urinalysis		X		
IWRS Subject Status Update		X		X
IWRS Weight Input (pediatric only)	X		X	X
IWRS Drug Dispensing	X	X	X	X
In Clinic Study Drug Administration ^o	X	X	X	
Outpatient Study Drug Administration ^o	WEEKLY			
Study Drug Compliance Review	X	X	X	X
Assessment of Pericarditis Recurrence	X	X	X	X
Adverse Event Reporting ^l	X	X	X	X

a The screening and enrollment visit can be combined.

- b Scheduling of visits within visit windows requires cautious planning to ensure there is no interruption to subject evaluation and study drug treatment.
- c Full physical examination includes at minimum evaluation of vital signs, head, eye, ear, nose, and throat as well as cardiovascular, dermatological, musculoskeletal, respiratory, GI, genitourinary, and neurological systems. The decision to perform examination of genitourinary system should be guided by clinical judgement.
- e ECHO is required to be obtained according to the central core lab parameters and then read locally and submitted to the central core lab for separate review and analysis.
- h Lipid panels are non-fasting and are to be drawn at a minimum of every 6 months during the randomization withdrawal and LTE periods, or more frequently as needed, with mandated evaluations as detailed in the schedule of events.
- j For women of child bearing potential - urine pregnancy testing can be repeated as needed throughout the course of the study and serum pregnancy can be drawn as needed; urine pregnancy is required to be performed at enrollment and 6 weeks after the last dose of study drug.
- l Adverse event reporting begins following the subject providing informed consent.
- m All procedures are to be completed prior to study drug administration.
- o Study drug administration is once weekly with a minimum of 5 days required between doses.
- z The MRI to occur only if the previous MRI was done longer than 6 months ago.

Table 7: Study Schedule of Activities – Supplemental Visits

Visit Name	PERICARDITIS RECURRENCE ASSESSMENT	END of TREATMENT (EOT)^x	SAFETY FOLLOW UP (SFU)^y (6 weeks post last dose)
Visit Window^b (days)	N/A	N/A	+/- 2
Visit Type	Clinic	Clinic	Clinic or TC/RN
Concomitant medications	X	X	X
Pericarditis Concomitant medications	X	X	X
Full Physical Examination ^c		X	
Abbreviated Physical Examination ^d	X		
Body weight and height	X		
12-Lead ECG	X	X	
Echo ^e	X ^e	X	
MRI (substudy only)		X ^z	
Pericardial pain (11-point NRS)	X	X	
EQ-5D	X	X	
SF-36	X	X	
ISI	X	X	
PGIPS	X	X	
PGA-PA	X	X	
Hematology, Chemistry Labs (Central)		X	
Lipid Panel (Central) ^h		X	
CRP (Local)	X		
CRP(Central)	X	X	
PK (Central)	X	X	X
ADA (Central)	X	X	X
Biomarkers (Central)	X	X	
Urine Pregnancy ^j (Local or Central)			X
Urinalysis		X	
IWRS Subject Status Update	X ^s	X	
IWRS Weight Input (pediatric only)	X		
IWRS Drug Dispensing	X		

Statistical Analysis Plan

Kiniksa Pharmaceuticals, Ltd.
Study KPL-914-C002

Visit Name	PERICARDITIS RECURRENCE ASSESSMENT	END of TREATMENT (EOT)^x	SAFETY FOLLOW UP (SFU)^y (6 weeks post last dose)
Visit Window^b (days)	N/A	N/A	+/- 2
Visit Type	Clinic	Clinic	Clinic or TC/RN
Study Drug Compliance Review	X	X	
Assessment of Pericarditis Recurrence	X	X	X
Adverse Event Reporting ^l	X	X	X

- b Scheduling of visits within visit windows requires cautious planning to ensure there is no interruption to subject evaluation and study drug treatment.
- h Lipid panels are non-fasting and are to be drawn at a minimum of every 6 months during the randomization withdrawal and LTE periods, or more frequently as needed, with mandated evaluations as detailed in the schedule of events.
- j For women of child bearing potential - urine pregnancy testing can be repeated as needed throughout the course of the study and serum pregnancy can be drawn as needed; urine pregnancy is required to be performed at enrollment and 6 weeks after the last dose of study drug.
- l Adverse event reporting begins following the subject providing informed consent.
- s PK at enrollment/baseline will be taken from ADA.
- x An EOT visit is to be conducted throughout the course of the study when a subject permanently discontinues study drug.
- y An SFU is required to be conducted within 6 weeks of the last dose of riloncept at any time throughout the course of the study including the RI period, the RW period, and the LTE period.
- z The MRI to occur only if the previous MRI was done longer than 6 months ago.

13.2. Missing Data Imputation Rules

Partial missing dates will be imputed for start/stop dates of AE and prior/concomitant medications, as well as start date of each pericarditis episode according to the rules below.

Table 8: Imputation Rules for Partial Missing Dates

Category	Scenario	Rule for missing dates
General rule	All	If year is missing, do not impute, unless otherwise specified
AE and prior/concomitant medication start date	Day is missing and (month, year) same as the first dose date	The day will be imputed as the same day of the first dose day or stop date, whichever is earlier.
	Day is missing and (month, year) not the same as the first dose date	The day will be imputed as the first day of the month or stop date, whichever is earlier.
	Month and day missing, year the same as the first dose date	Date will be imputed with the first dose date or stop date, whichever is earlier.
	Month and day missing, year different from the first dose date	Impute with the first day of the year.
AE and prior/concomitant medication end date	Day is missing	Impute with min(last day of the month, data cutoff, end of study date)
	Day and month are missing	Impute with min(last day of the year, data cutoff, end of study date)
	Entirely missing	Impute with min(data cutoff, end of study date)
First pericarditis episode start date	Day missing	Use first day of the month
	Month missing	Use January 01
Second or later pericarditis episode start date	Day missing	Use max(first day of the month, stop day of previous episode +1)
	Month missing	January 01
Other	Non-specific	For missing data handling rules not covered in this table, they will be defined in the ADaM Define file.

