5.1.3. Baseline Disease Characteristics

Baseline disease characteristics include the following:

- Oral corticosteroid use at RI Baseline (yes/no)
- Diagnosis of recurrent idiopathic pericarditis at RI (yes/no)
- Type of recurrent Pericarditis
 - Idiopathic
 - Pericardiotomy syndrome
 - Dressler's syndrome
 - Still's disease
 - Other
- Duration of disease from first episode to the date of informed consent
- Total number of pericarditis episodes, total number of episodes in the past year until first injection in the RI period, and annualized number of episodes per year,
- Time since beginning of qualifying episode in days
- Baseline central CRP value and weekly pain NRS score
- Baseline pericardial rub, effusion, tamponade, electrocardiogram (ECG) findings (widespread ST-elevation and PR-Depression), ECG interpretation
- Pericarditis treatment at baseline
 - Analgesics
 - Non-opioid analgesics
 - Opioid analgesics
 - Nonsteroidal anti-inflammatory drug (NSAIDs)
 - Aspirin

- Other NSAIDs
- Colchicine
- Corticosteroids
 - Oral corticosteroids
 - IM/IV corticosteroids
- Other

Disease characteristics for the qualifying episode, including the following:

- Number and proportion of subjects with presence of pericarditis pain, pericardial rub, new widespread ST-segment elevation or PR-segment depression on ECG, new or worsening in pericardial effusion, and pericardial inflammation on magnetic resonance imaging (MRI).
- Values of pain level, CRP (mg/dL), fever (Celsius), white blood cell (WBC; $10^3/\mu\text{L}$), and erythrocyte sedimentation rate (ESR) (mm/hr).
- Treatment for the qualifying episode
 - Analgesics
 - Non-opioid analgesics
 - Opioid analgesics
 - Nonsteroidal anti-inflammatory drug (NSAIDs)
 - Aspirin
 - Other NSAIDs
 - Colchicine
 - Corticosteroids
 - Oral corticosteroids
 - IM/IV corticosteroids
 - Other

The categorical (discrete) variables will be summarized using counts and percentages. The continuous variables will be summarized using n, mean, median, standard deviation, and range (minimum, maximum). Summaries will be presented for the RI, RW, and LTE periods.

Baseline disease characteristics will also be summarized for subjects who are on corticosteroid at RI baseline. In addition to those specified above, the following baseline data will be summarized:

- Duration (in weeks) of using oral corticosteroid prior to enrollment
- Average dose (mg/day) of oral corticosteroid prior to enrollment

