- Cumulative dose (mg) of oral corticosteroid prior to enrollment

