5.1.5. Prior and Concomitant Medications

Prior medications are defined as those taken before the date of the first study drug administration, i.e. started before the start of the study drug.

Concomitant medications are defined as any non-study medication taken during the treatment period which is from the date of first dose to the date of last dose plus 6 weeks.

Additionally, the medications will be considered concomitant if the start date of the medication is missing.

A medication that started prior to the first dose of the study drug and continued after that date will be considered as both prior and concomitant.

Prior and concomitant medications will be coded using World Health Organization (WHO) Drug (version March 2018). Medications will be summarized by ATC level 2 code and preferred term. Summary will be done by periods (i.e., RI, RW, and LTE) and by treatment (KPL-914 vs placebo) for RW period. One subject will be counted once within one preferred term and one ATC class. The medication information will be presented in a by-subject listing with ATC class (level 2) and WHO Drug Dictionary preferred term, start and stop date, dosage, route, frequency and indication.

Concomitant pericarditis treatment will be summarized by period and by treatment for RW period using the following categories:

- Analgesics
 - Non-opioid analgesics
 - Opioid analgesics
- Nonsteroidal anti-inflammatory drug (NSAIDs)
 - Aspirin
 - Other NSAIDs
- Colchicine
- Corticosteroids
 - Oral corticosteroids
 - IM/IV corticosteroids
- Other

In addition, concomitant pericarditis treatment received during the RW treatment period will also be summarized based on the status of receiving bailout treatment (i.e. concomitant

medication received before start of bailout treatment vs after start bailout treatment) for each treatment group in the RW period.

For RI period, use of concomitant pericarditis treatment (i.e., background treatment) will be summarized over time.

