5.2.3.1. Secondary Endpoints in the RI Period

The following efficacy endpoints will be included for the RI period. Unless specified otherwise, change means change from RI baseline to RI week 12, and the denominator for a proportion is the total number of subjects who were treated in the RI period.

1. Time to pain response, defined as number of days from first dose to the first day a subject’s daily pain NRS is ≤ 2 of the 3 days over which, the rolling average daily pain NRS is ≤ 2 . Subjects with baseline NRS ≤ 2 will be excluded from the analysis. If one or more daily NRS score is missing, rolling average will be considered not meeting the response criteria.
2. Time to CRP normalization (≤ 0.5 mg/dL)

Time to CRP normalization will be censored at treatment discontinuation, taking prohibited medication, or week 12, whichever occurs first. Subjects with baseline CRP ≤ 0.5 mg/dL will be excluded from the analysis.

3. Time to riloncept monotherapy

Time to riloncept monotherapy is defined as number of weeks from first dose to the first day of achieving monotherapy. Subjects without background therapies at RI baseline will be excluded from the analysis.

4. Time to treatment response defined as time from first dose to the first day of pain response (defined in endpoint 1 above), and CRP ≤ 0.5 mg/dL within 7 days before or after pain response. Treatment response day will be the day of pain response, whether pain response occurs before or after CRP ≤ 0.5 mg/dL.
5. Proportion of subjects achieving clinical response at RI week 12 based on RIS analysis set

Subjects who stopped background SOC pericarditis therapy on or before week 10, as well as who achieve CRP ≤ 0.5 mg/dL and weekly average of daily pericarditis pain score ≤ 2.0 on the 11-point NRS within the 7 days prior to and including the day of randomization on RI Week 12/Randomization are responders.

Additional analysis will be done base done the completers who finished the 12-weeks of RI treatment.

6. Number (percentage) of subjects with normalization of CRP (≤ 0.5 mg/dL) at RI Week 12. Subjects with baseline CRP > 0.5 mg/dL in the RI analysis set will be used in the analysis.
7. Change from baseline in pericarditis weekly pain score at RI Week 12 and over time.
8. Change from baseline in CRP level at RI Week 12 and over time.
9. Proportion of subjects with resolution of echocardiographic and ECG abnormalities (yes/no) at RI Week 12.

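### Table 8 applies the adverse-event start-date rule to medications, so a drug already in use at first dose can lose its prior status and its pre-dose duration

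*SAP*

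**What the plan says.** Section 13.2, Table 8 (SAP v2.0) puts both kinds of record in one block, "AE and prior/concomitant medication start date". Three of its rows matter here:

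- Day missing, month and year equal to those of first dose: "The day will be imputed as the same day of the first dose day or stop date, whichever is earlier".
- Month and day missing, year equal to that of first dose: "Date will be imputed with the first dose date or stop date, whichever is earlier".
- Month and day missing, any other year: "Impute with the first day of the year".

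Section 5.1.5 defines a prior medication as one that "started before the start of the study drug". A drug that began earlier and continued counts as both prior and concomitant. The only clause there on a missing start date makes the drug concomitant and says nothing about prior status.

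For subjects on corticosteroid at run-in (RI) baseline, Section 5.1.3 plans "Duration (in weeks) of using oral corticosteroid prior to enrollment" and "Cumulative dose (mg) of oral corticosteroid prior to enrollment", together with the average daily dose. It gives no derivation for any of them.

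**The concern.** For an adverse event, moving a doubtful start to the first dose is the cautious choice, because the event is then counted as treatment-emergent. For a medication the same move discards known pre-study use. A background drug is by definition already being taken at first dose, and Section 11.1 notes that subjects entered with a qualifying episode and on background therapy. Treatment begun for a recent episode can easily have started in the month or year of first dose, which is where the rule acts.

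At stake are the prior-medication tables and possibly the description of corticosteroid exposure before enrollment. Oral corticosteroid use at RI baseline is also a stratification factor, so readers will look at that description.

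**Working it through.** The SAP states no figure on this point, so there is none to reproduce. The check applies the Table 8 rules and the Section 5.1.5 test (prior if start < first dose) to partial dates.

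**Rule.** For a start known only to the month or year of first dose, imputed start = min(first dose, stop). For an ongoing drug this is the first dose date. The test start < first dose then fails, and pre-dose days = first dose − start = 0.

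**Results.** The first-dose dates are assumed, for illustration. Cells give pre-dose days; the last row counts start and stop day inclusively.

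| Drug and recorded start | 20 Feb 2019 | 20 Jun 2019 | 20 Dec 2019 | Prior? |
|---|---|---|---|---|
| Ongoing, month of first dose | 0 | 0 | 0 | No |
| Ongoing, year of first dose only | 0 | 0 | 0 | No |
| Ongoing, month before first dose | 50 | 50 | 49 | Yes |
| Ongoing, previous year only | 415 | 535 | 718 | Yes |
| Stopped 5 days before first dose, year of first dose only | 1 | 1 | 1 | Yes |

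The most that can be lost in the first row is 19 days in each case. In the second row it is 50, 170 or 353 days. The rule also jumps: with first dose on 20 June 2019, a start recorded as 2019 gives 0 days and one recorded as 2018 gives 535.

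For pericarditis episodes, Table 8 itself uses the first of the month or 1 January (for a later episode with the day missing, not before the day after the previous episode stopped). An episode and the drug given for it, both known only to the month of first dose, can therefore receive different dates.

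**Average loss per affected record.** Assumption: the true start is uniform between the earliest possible date and first dose.

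- Year only, first dose on day D uniform over 1–365: mean loss = E(D)/2 = 183/2 = 91.5 days, and 91.5/7 = 13.1 weeks. Simulation gives a median of 9.8 weeks and a maximum of 52.
- Month known: simulation gives a mean loss of 7.8 days. As a check, with an average month of 365/12 = 30.4 days, the mean day of the month is (1 + 30.4)/2 = 15.7, and half of that is about 7.8.

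**Effect on a group mean.** The share of affected corticosteroid users is not given; 10% is assumed.

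- Month known: 0.10 × 7.8 = 0.78 day, and 0.78/7 = 0.1 week.
- Year only: 0.10 × 13.1 = 1.3 weeks.

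If the corticosteroid variables come from these dates, an affected ongoing record adds 0 to duration and 0 to cumulative dose, and its average dose is undefined (0/0). Records with full dates are unchanged.

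**The case against.** The strongest reply is that little is lost. Because the rule takes the earlier of first dose and stop date, a drug with a known stop before first dose remains prior. Concomitant status is never affected. Background therapy also appears elsewhere: Section 5.1.3 tabulates pericarditis treatment at baseline and for the qualifying episode, and Section 5.1.5 summarises RI background treatment over time. All of this stands. It limits the damage to the prior label and to pre-dose durations; it does not make the rule right.

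A reader might infer that affected subjects also drop out of the corticosteroid-at-baseline summary, or out of time to monotherapy (RI endpoint 3), where "Subjects without background therapies at RI baseline will be excluded from the analysis". The SAP does not support that. The loading dose is given at the RI baseline visit, so a drug dated to that day is still in use at RI baseline. Exclusion would need a strict started-before-first-dose derivation, which the SAP does not state. Corticosteroid use at RI baseline is also captured as a yes/no randomization factor.

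It can also be said that the corticosteroid exposure variables may not use these records. The schedule lists pericarditis history and pericarditis medications separately from other concomitant medications, and no derivation is given. That is fair, and this part of the point is conditional. The SAP names no other source, however, and the closing row of Table 8, which defers to the ADaM Define file, covers only rules that the table does not contain.

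**Conclusion.** The point holds in a limited form. For a drug still taken at first dose whose start is known only to the month or year of first dose, Table 8 read with Section 5.1.5 removes prior status and gives 0 pre-dose days. For a drug with such a start and a known earlier stop, it reduces the course to 1 day.

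The consequence is descriptive: the prior-medication tables and, conditionally, corticosteroid duration and dose before enrollment. Stratification, the primary log-rank test and the major secondary analyses are not shown to be affected.

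The size cannot be fixed from the SAP. The range of 0.1 to 1.3 weeks in mean prior corticosteroid duration rests on the assumed 10% and on uniform dates. The upper end needs every affected record to be year-only. With no partial dates the effect is nil.

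**What to change.** In Table 8, restrict the two first-dose-date rows to adverse events and add a medication rule:

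- For drugs recorded as background or qualifying-episode therapy, or otherwise known to have been taken before study drug, keep prior status, and concomitant status as well if continued.
- Impute the start within the recorded month or year, before first dose and never after the stop date. One option is the first of the month or 1 January, as Table 8 already does for other months and years.
- Let the recorded pre-study use decide prior status, so that a first dose on the first of a month does not recreate the problem.
- Footnote how many durations and doses rest on an imputed start.

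A midpoint between the earliest possible date and the day before first dose would need a cap at the end of the recorded month or year. Without one, a start recorded as 2017 with first dose on 20 June 2019 would be imputed to about 26 March 2018.

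The cost is two edited rows and one derivation, with no new data. The downsides are separate date rules for medications and adverse events, and that the earliest-date choice gives the longest duration consistent with the record.
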